**E. Determination of Eligibility**

Once Informed Consent has been obtained, the subject's eligibility to continue study participation will be determined by the study inclusion/exclusion criteria. This may include an interview to assess significant subject medical/surgical history, history of present illness/injury, evaluation of present pain and functional capacity, and a radiographic assessment. Evaluation of the inclusion/exclusion criteria will be documented on the Inclusion/Exclusion Criteria case report form. Subjects that do not meet all inclusion/exclusion criteria will be terminated from the study and no further study data will be collected. A Study Completion form will be completed and the reason for termination must be specified on the form. These subjects will be excluded from the primary statistical analysis for this study.

**F. Monitor Log**

The Site Monitoring Visit Log (Appendix C) will be maintained throughout the course of the study. The log will contain the visit date, monitor name/signature and the purpose of the visit (i.e. site initiation, onsite interim monitoring (as applicable), site close-out, etc.). The site monitoring visit log will be filed in the site Regulatory Binder for the study.

**G. Delegation of Authority (Site Signature Log)**

A Site Signature Log (Appendix C) will be maintained throughout the study and will contain the names, initials, signatures and study responsibilities of all site personnel/designees involved in study procedures and data collection. The Site Signature Log will be filed in the site Regulatory Binder for the study.

**H. Baseline/Pre-operative Assessment**

Baseline/pre-operative data will be collected on the following case report forms:

1. Inclusion/Exclusion Criteria
2. Demographic Evaluation
3. Physical Exam
4. EQ-5D
5. Knee Society Score
  - a. Surgeon completed
  - b. Patient completed
6. Protocol Deviations (as applicable)
7. Study Completion (as applicable)

**I. Surgical Technique**

Standard operative procedures will be followed and all surgical procedures will be performed under aseptic conditions. Investigators will implant all commercially available *Persona* fixed bearing components and any other compatible products in compliance with corresponding labeling requirements and in accordance with appropriate surgical technique(s).

**J. Intention to Treat**

Subjects who are enrolled in the study with an intention to treat (i.e. underwent the study Informed Consent process, signed and dated the Informed Consent, and met the study inclusion/exclusion criteria), but do not undergo the study surgery due to subject withdrawal, investigator withdrawal, or any other reason(s), will be terminated from the study. A Study Completion form will be completed and the reason for termination must be specified on the form. These subjects will be excluded from the primary statistical analysis for this study.

**K. Surgical and Immediate Post-surgical Procedures (Data Collection)**

Surgical and immediate post-surgical data will be collected on the following case report forms:

1. Operative Information
2. Surgical Device Information
3. Discharge Summary
4. Adverse Event Report (as applicable)
5. Protocol Deviations (as applicable)
6. Study Completion (as applicable)

Post-surgical management for study subjects will follow the investigator's standard of care for patients undergoing total knee arthroplasty (e.g. prophylactic antibiotic therapy, prevention of deep vein thrombosis, prevention of pulmonary embolism, etc.). Post-surgical rehabilitative therapy will be as prescribed by the investigator.

**L. Post-operative Follow-up Procedures (Data Collection)**

Post-operative clinical evaluations/assessments will be conducted at the following visit intervals:

Clinical Interval	Interval Window in Days Post-op*	Approximate Window in Weeks or Months Post-op*
6 weeks	17 to 90 days	-4 weeks / +7 weeks
6 months	91 to 244 days	-3 months / +2 months
1 year	245 to 547 days	-4 months/ +6 months
2 years	548 to 912 days	-/+ 6 months
3 years	913 to 1277 days	-/+ 6 months
4 years	1278 to 1642 days	-/+ 6 months
5 years	1643 to 2007 days	-/+ 6 months

\*Visit(s) outside of window will be determined based on Days Post-op

Post-operative clinical data will be collected on the following case report forms:

1. Physical Exam
2. FJS-12 (Forgotten Joint Score)
3. EQ-5D
4. Knee Society Score
  - a. Surgeon completed
  - b. Patient completed
5. Physician Assessment of Post-op Radiographs
6. Adverse Event Report (as applicable)
7. Protocol Deviations (as applicable)
8. Study Completion (as applicable)

Subjects will be followed post-operatively for up to 5 years. Unless the study is otherwise closed, data will continue to be collected until the subject completes the study per the protocol, voluntarily withdraws from the study, is withdrawn from the study by the investigator, is lost to follow-up, undergoes revision to remove a study device, or expires. See Management of Incurrent Events (Section IX, Subsection D of this protocol) for additional details. Reason(s) for study completion must be documented on the Study Completion case report form.

**M. Minimization of Subjects Lost to Follow-up**

Subject follow-up is extremely important for the conduct of a clinical study, and the expectation is to maintain the highest possible rate of follow-up compliance throughout this study. At each follow-up interval, subjects should be counseled on the importance of completing future study follow-up intervals.

#### ***N. Radiographic Definitions and Methods***

All postoperative radiographic evaluations performed according to the protocol will be reviewed by the Investigator at the time of the evaluation and documented using the Physician Assessment of Post-op Radiographs case report form. This includes documentation of any significant radiographic findings. In addition, an Adverse Event Report case report form must be completed for those findings indicated by an asterisk on the Physicians Assessment of Post-op Radiograph case report form, or for any other findings identified as an adverse event.

1. Required radiographic views

Standing anteroposterior (AP) and standard lateral radiographs of the operative knee are required to be captured at the 6 week, 6 month, 1 year, 2 year, 3 year, 4 year, and 5 year follow-up visits.

Radiographs should have similar exposure and must show the entire study device and surrounding bone. For consistency, every effort should be made to capture all radiographic views for a given subject using the same institution throughout the study. However, radiographs captured at a different institution may be used for the study, provided they meet required study specifications and are captured within the required interval window. The investigative site will retain copies (hard copy/CD/digital) of all radiographs referenced for the study.

2. Submission to Sponsor

At Sponsor's discretion, study radiographs may be requested from the sites for independent radiographic review and assessment of appropriate parameters.

#### ***O. Recommended Revision Procedure***

See Management of Incurrent Events (Section IX, Subsection D of this protocol)

### **IX. Reporting**

The management of all study data received by Sponsor will be the responsibility of Sponsor or its Designee. The use or disclosure of all protected health information will comply with the Health Insurance Portability and Accountability Act (HIPAA). All information will be treated with strict adherence to professional standards of confidentiality and will be filed by Sponsor under adequate security and restricted accessibility by clinical personnel. All electronic systems used to create, modify, maintain, or transmit study records will be validated according to 21 CFR Part 11(iii). Reports and communications relating to study subjects will typically identify each subject only by the subject's initials, assigned study subject Case ID number, date of surgery, operative side, and date of birth.

#### ***A. Prior to Initiation of the Study***

1. Clinical Trial Agreement (CTA)

A fully executed (signed by all required parties) CTA must be on file with Sponsor prior to any investigator participating in this study.

2. Institutional Review Board/Ethics Committee Protocol Approval  
This study protocol must be submitted to and approved by the Investigator's Institutional Review Board (IRB) or Ethics Committee (EC). A copy of the IRB or EC approval letter must be submitted to Sponsor. The letter should identify the following:
  - Protocol name and/or number
  - Date of IRB or EC meeting (if available)
  - Date of approval
  - Date of expiration
  - Signature of IRB or EC
3. Informed Consent  
A Sponsor-approved Informed Consent document (Appendix A Sample) will be provided along with the study protocol for IRB or EC submission and approval. If the IRB or EC requires revisions to the provided Informed Consent, the requested revisions must be submitted by the Investigator to Sponsor for review and approval. Once Sponsor has reviewed and approved the revision, the Informed Consent will be re-submitted to the IRB or EC for final review and approval. A copy of the final IRB or EC approved Informed Consent form (ICF) must be submitted to Sponsor.

**B. Clinical Data Collection/Submission**

1. Summary of Case Report Form Data Collection  
Study data will be collected on study-specific Case Report Forms (CRFs) provided by Sponsor. For subjects having bilateral knee replacement, separate case report forms must be completed for each operative side.  
  
The following CRF guidelines should be followed:
  - Complete carefully and accurately.
  - Complete header information consistently across all case report forms for each individual study subject.
  - Use the study subject's initials in header section.
  - Use the study subject's unique Case ID number assigned as instructed.
  - Do not provide information that is not requested on the CRFs.
  - Ensure that all fields are completed. For fields completed by the subject, efforts should be made to obtain any missing responses prior to the subject completing their visit.
2. Data Submission  
Completed CRFs will be submitted directly to Sponsor by electronic data capture and submission via a method approved by Sponsor. Every effort must be made to ensure data submission to Sponsor is made within 30 days of the visit completion.
3. Quality Assurance of Data  
The Investigator should ensure the accuracy, completeness, legibility, and timeliness of the data reported to the Sponsor in the CRFs and in all required reports. Data reported on the CRF, which are derived from source documents, should be

consistent with the source documents or the discrepancies should be explained. All electronic systems used to create, modify, maintain, or transmit electronic study records will be validated according to 21 CFR Part 11(iii). Sponsor will maintain quality control systems, in accordance with Sponsor's policies and procedures.

### **C. Reporting Requirements**

#### **1. Investigator Reporting Responsibilities**

The Investigator should ensure the accuracy, completeness, legibility, and timeliness of data reported to the Sponsor in accordance with this protocol. The Investigator or Designee will provide periodic reports to their IRB or EC as required to maintain IRB or EC approval throughout the study, and will provide any required final reporting to the IRB or EC upon study completion/termination. A copy of all IRB or EC re-approval letters must be submitted to the Sponsor. If the IRB or EC terminates or suspends its approval of the study, the Investigator or Designee will suspend study-related activities and will promptly notify the Sponsor. The Investigator should also promptly provide written reports to the Sponsor and the IRB or EC regarding any changes significantly affecting the conduct of the study, and/or increasing risk to the subjects.

#### **2. Retention of Records**

Study records must be retained by the Investigator or Designee for a minimum of 2 years from the Investigator's study termination date, or per applicable regulatory and/or IRB or EC requirements (whichever time period is greater). Measures shall be taken to prevent accidental or premature destruction.

### **D. Management of Incurrent Events**

#### **1. Failure to Obtain Informed Consent**

Study data will not be collected until the Informed Consent has been signed and dated by the candidate. If a candidate does not wish to participate (does not sign and date the Informed Consent), data for that candidate will not be collected for this study.

#### **2. Adverse Events**

An adverse event is any unfavorable or unintended sign, symptom, or disease associated with the use of the study device, whether or not related to the device. Adverse event is synonymous with complication or medical event.

See Section IX, Subsection E of this protocol for additional information regarding adverse event classifications. All medical events, regardless of classification, are required to be reported on the Adverse Event Report case report form. The completed Adverse Event Report case report form must be submitted to Sponsor in a timely manner. The Investigator or Designee will also promptly provide Sponsor with any additional requested information required for Sponsor to comply with regulatory requirements. If applicable per their reporting requirements, the Investigator or Designee will also report applicable adverse event(s) to their IRB or EC.

3. Revision

In the event that removal of one or more of the study knee components is necessary, the Investigator will determine the best treatment and/or revision method for the subject.

Prior to revision surgery, the Investigator or qualified Designee must document any significant radiographic findings related to the need for revision on the Physician Assessment of Postop Radiographs case report form. An Adverse Event case report form must be completed for those findings indicated by an asterisk on the Physicians Assessment of Postop Radiograph case report form.

Once the revision surgery has been completed, the Investigator or qualified Designee must complete an Adverse Event case report form as well as a Study Completion case report form terminating the subject from the study. For the study completion status, select “Study Prosthesis Removed”. This procedure also applies to partial revisions such as polyethylene exchange.

4. Investigator Withdrawal

The Investigator can choose to withdraw a subject from the study if the subject no longer meets study inclusion/exclusion criteria. The reason for the Investigator’s withdrawal of the subject must be documented on the Study Completion case report form.

5. Subject Withdrawal

Study subjects may choose to withdraw from the study at any time, for any reason. If possible, a final evaluation will be completed for any subject who no longer wishes to participate in the study. The reason for the subject withdrawal must be documented on the Study Completion case report form.

6. Lost to Follow-up

A study subject will be considered lost to follow-up after they have missed a visit and attempts to locate and evaluate the subject using the procedure outlined below have failed. All attempts to contact the subject are to be documented in the subject’s medical record and on the Study Completion case report form. Missed visit(s) also must be documented using the Protocol Deviations case report form. The first three contact attempts should be made by telephone, with additional attempts as outlined in the following table:

If	Then
a response is not received after three (3) phone calls	the Investigator or Designee should send a letter to the subject explaining the follow-up agreement per the Informed Consent, and requesting a response from the subject.
all attempts to contact the subject are unsuccessful or the subject is contacted and chooses to withdraw from the study	a Study Completion case report form will be completed and will specify the reason the subject is no longer participating in this study.

7. Protocol Deviations

Investigators should not deviate from the study protocol. If a protocol deviation does occur, the deviation must be documented on the Protocol Deviation case report form and submitted to Sponsor. If applicable per their reporting requirements, the Investigator or Designee will also report applicable protocol deviations to their IRB or EC.

8. Study Termination

Study subject participation is expected to end upon completion of the subject's 5-year follow-up visit unless the subject voluntarily withdraws from the study, is withdrawn from the study by the Investigator, is lost to follow-up, undergoes revision to remove a study device, or expires. Reason(s) for study completion must be documented on the Study Completion case report form.

If Sponsor decides to terminate the study early, Sponsor will inform the Investigators of the reason for early study termination. It is the responsibility of the Investigators to inform their IRB or EC as applicable according to local and national laws/regulations.

9. Modification of the Protocol

All amendments to this clinical protocol shall be agreed to by Sponsor and be recorded with a justification for the amendment prior to implementation. Approval of the applicable IRB or EC must be obtained prior to implementation, if required according to the local and/or national laws/regulations.

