A Serious Adverse Device Effect is an adverse device effect that has resulted in any of the consequences characteristic of a serious adverse event.

Sponsor is responsible for determining the final classification of adverse events.

If an Unanticipated Serious Adverse Device Effect (USADE) is identified by Sponsor, it will be promptly reported to concerned Investigators and regulatory authorities as required by applicable regulatory requirements. If applicable per their reporting requirements, the Investigator or Designee will report the USADE to their IRB or EC.

2. Intensity of Symptoms

Mild:

The subject is aware of the sign or symptom, but finds it easily tolerated. The event is of little concern to the subject and/or little clinical significance. The event is not expected to have any effect on the subject's overall health or well being.

Moderate:

The subject has discomfort enough to cause interference with or change in usual activities. The event is of some concern to the subject's health or well being and may require medical intervention and/or close follow-up.

Severe:

The event interferes considerable with the subject's usual activities. The event is of definite concern to the subject and/or poses substantial risk to the subject's health or well-being. The event is likely to require medical intervention and/or close follow-up and may be incapacitating or life threatening. Hospitalization and treatment may be required.

**NOTE:** The term "severe" refers to the intensity of the event and can be used with any event, without regard to whether or not it meets the criteria for being classified as "serious" or "unanticipated". For example, a subject can have a severe headache, but it is not a serious event.

3. Outcome Definitions

The outcome is in relationship to the Adverse Event, not the treatment rendered for the event (if any).

Resolved:

The adverse event has been resolved and/or no further treatment is required to treat the reported condition or illness.

Tolerated:

The adverse event will most likely never be resolved. The subject "tolerates" the illness or condition as a matter of life.

Pending:

Treatment or diagnostic studies were prescribed for the adverse event and the outcome of the adverse event is not yet known.

Study Withdrawal:

Due to the adverse event, the subject was withdrawn from the study.

Device Removal:

The adverse event resulted in the removal of a study device.

Reoperation of Affected Joint:

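### IX.D.4 lets pre-operative eligibility criteria end follow-up after implantation, and a later device removal would then have no route into the survivorship analysis; the frequency is unknown and the likely effect small

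*Combined protocol and SAP*

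**What the plan says.** IX.D.4 reads: "The Investigator can choose to withdraw a subject from the study if the subject no longer meets study inclusion/exclusion criteria". It does not separate the time before surgery from the time after. The only record it requires is the reason: the investigator's "withdrawal of the subject must be documented on the Study Completion case report form".

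The rule reaches into follow-up. VIII.L, on post-operative data collection, says collection continues until, among other exits, the subject "is withdrawn from the study by the investigator, is lost to follow-up, undergoes revision to remove a study device, or expires". IX.D.8 repeats the list for the end of participation: "is withdrawn from the study by the Investigator, is lost to follow-up, undergoes revision to remove a study device, or expires". In both places investigator withdrawal and revision are separate exits.

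For a subject who chooses to leave, IX.D.5 asks for more: "If possible, a final evaluation will be completed for any subject who no longer wishes to participate in the study". That is a single assessment at exit, and IX.D.4 has no equivalent. IX.D.3 records a revision by an adverse event form and by a Study Completion form that terminates the subject, so it presupposes a subject who is still enrolled.

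Among the adverse event outcomes in IX.E.3, Study Withdrawal ("Due to the adverse event, the subject was withdrawn from the study") is distinct from Device Removal ("The adverse event resulted in the removal of a study device").

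Survivorship is defined by removal of a study device (IV), is the primary endpoint for sample size (XI.B), and is summarised by Kaplan-Meier (XI.A). No censoring rule or sensitivity analysis is given.

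**The concern.** The criteria in VI are screening criteria. Carried past implantation, they can turn a complication of the operation into a reason to stop observing the knee. A knee withdrawn for joint infection or suspected sensitivity to the implant may well have a higher removal risk than the knees that stay. Kaplan-Meier censoring assumes that its later risk is average. If it is not, the censoring is informative and the error runs one way, towards better survivorship. The confidence interval would not show it, and enrolling more knees would narrow the interval without reducing the bias. XI says the summaries may support regulatory submissions and publications, so the direction matters even in a descriptive study.

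**Working it through.** **Text check.** Exclusions in VI.B set beside risks in X.B:

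| Exclusion (VI.B) | Listed risk (X.B) |
|---|---|
| 2, infection | Infection |
| 3, inadequate bone stock | Bone resorption (osteolysis) |
| 8, severe instability from absent collateral ligaments | Instability; soft tissue damage |
| 10, sensitivity to implant materials | Metal sensitivity |
| 12, earlier arthroplasty of the same knee | None; met by every knee once implanted |

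These are examples. The last row shows that a literal post-operative reading cannot be intended, so the plan leaves open which post-operative changes count. The sections on withdrawal, revision, loss to follow-up, adverse events and study completion contain no request for device status after exit.

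**Size.** The plan has no figure to reproduce: XI.B gives only the endpoint and 10% attrition, not split by cause. What follows is an illustration.

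Inputs from the documents:
- At most 15 sites x 100 knees = 1,500 (I).
- At least 6 sites (V); at the 100-knee cap, 6 x 100 = 600.
- Follow-up of 5 years (VIII.L).
- Attrition of 10% (XI.B).

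Assumptions not in the documents:
- Five-year removal risk p of 2%, 3% or 5%.
- A share w of removals preceded by withdrawal, censored just before removal.
- Other attrition independent of removal risk and spread evenly, giving average retention of about 0.95.
- A plain 95% interval, because the plan names no method.

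Formulas:
- Reported survivorship = (1 - p)^(1 - w).
- Bias = (1 - p)^(1 - w) - (1 - p), roughly w x p.
- Half-width = 1.96 x sqrt(q(1 - q) / (0.95N)), with q = 1 - (1 - p)^(1 - w).

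Example at p = 3%:
- w = 5%: 0.97^0.95 = 97.15%, bias 0.15 points. Half-width 1.37 (N = 600) or 0.86 (N = 1,500).
- w = 10%: 0.97^0.90 = 97.30%, bias 0.30 points. Half-width 1.33 or 0.84.

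Bias in points, with half-widths for N = 600 / 1,500 in brackets:

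| p | w = 5% | w = 10% | w = 30% |
|---|---|---|---|
| 2% | 0.10 (1.12 / 0.71) | 0.20 (1.09 / 0.69) | 0.60 (0.97 / 0.61) |
| 3% | 0.15 (1.37 / 0.86) | 0.30 (1.33 / 0.84) | 0.89 (1.18 / 0.75) |
| 5% | 0.24 (1.75 / 1.11) | 0.49 (1.70 / 1.08) | 1.47 (1.51 / 0.96) |

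At w = 5% the bias is at most 22% of the half-width (0.244 / 1.105), and at w = 10% at most 45% (0.489 / 1.078). At w = 30% it about equals or exceeds the half-width only with 1,500 knees, or nearly equals it with 600 knees at 5% removal.

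Missed removals, N x p x w before attrition, at p = 3% and w = 10%: 600 x 0.03 x 0.10 = 1.8, and 1,500 x 0.03 x 0.10 = 4.5.

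**Cross-check with a delay.** A simulation of 2,000,000 knees assumed a 2% complication risk, half of complications leading to removal after a mean of 6 months, and a further 2% background removal risk. True survivorship was 97.1%. Kaplan-Meier gave 97.2% when 10% of complications led to withdrawal, 97.6% at 50% and 98.0% at 100%. With no complication-driven withdrawal the bias vanished.

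**The case against.** The strongest reply is that the documents show a permission and not a practice. IX.D.4 is discretionary, and a sensible investigator would hardly withdraw a patient because the joint became infected. This stands, and it limits the point to a conditional one.

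A reader might infer that the Study Withdrawal outcome in IX.E.3 proves the sponsor expects investigators to use IX.D.4 for complications. It does not. It shows that withdrawal because of an adverse event is foreseen, but not who decides or that eligibility is the reason.

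A reader might also infer from VIII.E ("These subjects will be excluded from the primary statistical analysis for this study") that a knee withdrawn later drops out of the primary analysis. That sentence concerns the eligibility check after consent, and the matching rule in VIII.J concerns subjects who never have the surgery. Neither covers an implanted knee withdrawn during follow-up.

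The loss of information is only partial. The complication itself must be reported (IX.D.2, IX.E), and the reason for withdrawal is recorded. The Study Completion form is not in the text available and may capture more at exit, but a form completed at exit cannot record a removal that happens afterwards.

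Finally, later device status is equally unasked for after subject withdrawal (IX.D.5) and loss to follow-up (IX.D.6). This is correct, and the remedy should cover all three exits. IX.D.4 still deserves separate mention: it is the exit tied to a change in eligibility, and it lacks even the final evaluation of IX.D.5.

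**Conclusion.** The gap is real and the effect is conditional. If an investigator withdraws a subject for a complication that matches a criterion and the device is later removed, the plan has no route for recording that removal, and Kaplan-Meier survivorship is overstated. This rests on the usual treatment of withdrawals as censored, which the plan does not state, and on such knees having an above-average removal risk.

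The size cannot be derived from the documents. At an assumed 3% removal risk and a 5-10% share it is 0.15 to 0.30 points, well inside a half-width of about 0.8 to 1.4 points. If such withdrawals are rare, it is negligible. A reader might infer from the 30% column that the bias could swamp the interval, but nothing in the documents supports a share that high. Nor do they support saying that survivorship will be overstated.

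The study is descriptive with no decision threshold, so this is a minor, inexpensive improvement and no threat to the study's validity.

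**What to change.** 1. State in IX.D.4 that, after implantation, a complication matching an eligibility criterion is not in itself a reason to end data collection. Withdrawal for other reasons stays available, such as joining another surgical study (exclusion 1) or inability to complete follow-up (inclusion 5).
2. Keep every implanted, eligible, consented knee in the survivorship analysis, and state the censoring rule.
3. After any post-operative exit (investigator withdrawal, subject withdrawal or loss to follow-up), ascertain device status through 5 years where consent and the IRB/EC allow.
4. Add a worst-case sensitivity analysis that counts post-operative withdrawals linked to a device- or joint-related adverse event as removals. The Study Completion reason and the Study Withdrawal outcome, both already collected, identify them. Report it as a bound and not as a corrected estimate. Each such knee lowers five-year survivorship by about 100/600 = 0.17 points with 600 knees, or 100/1,500 = 0.07 with 1,500.

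The cost is a short amendment with IRB/EC review where required, a few status checks, one extra table and possibly a slightly less favourable survivorship figure. Item 4 uses existing data and could proceed without the amendment. All four items concern data collection and analysis only; treatment decisions are unaffected.
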